8.2 SAFETY ASSESSMENTS

In accordance with applicable regulatory requirements and principles for the ethical conduct of research, a Safety Officer will be appointed by the NIA to oversee the safety of study participants.

Because the study population has, per the eligibility criteria, a limited expected prognosis of less than one year, death and the preceding associated development of symptoms related to the natural progression of disease are expected. Because the study setting is home hospice, hospitalizations related to the natural progression of disease are expected to be unusual. However, deaths, hospitalizations, and emergency department visits will be monitored.

Because the focus of the trial educational intervention focuses on medication-related management, review and support, medication changes and symptom changes potentially related to drug related problems (DRPs) will be monitored, including potential DRPs present upon study enrollment which, by definition, are not related to the research.

Medication changes will be identified by collecting medication lists every 2 weeks and iteratively identifying changes between lists. DRPs will be monitored by a trained research assistant who will screen the medical record using a Screening Algorithm of Potential Drug Related Problems at *study enrollment and every 2 weeks up to 2 months* for a retrospective chart review, and then monthly up to 6 months. These medical record will be reviewed for new clinical events, symptoms, abnormal lab events and drug levels, new reported drug allergies or drug associated problems identified by clinicians. Secondarily, a trained research assistant will also conduct a screening telephone interview with patients (or their caregiver, if patient is unable to participate) for potential DRPs using a method by Chrischilles³¹ *at 2 weeks and monthly* thereafter.

To ensure that potential DRPs, emergency department visits, hospitalizations and deaths are indeed unrelated to the research, these will be closely monitored by the study's Event Classification Pharmacist (ECP) comprised of a pharmacist using a procedure described below in Section 8.3.

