2.3 RISK/BENEFIT ASSESSMENT

2.3.1 KNOWN POTENTIAL RISKS

The risks and costs vs benefits of reducing polypharmacy for patients with advanced disease and their family caregivers remains a genuine clinical uncertainty. Multiple studies support the use of myriad individual chronic disease medications, such as statins, in elderly adults with appropriate indication. However, the benefit of continuing chronic disease medications after hospice admission on quality of life, family caregiver medication hassle, or patient survival is unknown. Simplifying medication regimens through a process of deprescribing is one remedy to medication complexity as death approaches, but may be associated with potential risk of stress to family caregivers about making decisions regarding stopping medications and additional potential risk of adverse drug withdrawal events after stopping medications - a particular concern when abruptly stopping medications with long half lives that are known to require tapering protocols.

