In general, hospice staff (i.e. front-line hospice nurses or local administrative staff) will preliminarily screen eligible patients on their daily hospice census list and, at their discretion within the first week after the hospice admission visit, provide an *IRB-approved generic brochure* about research in hospice and palliative care; if there is interest in learning more about the study, the patient and family caregiver will also be given an IRB-approved study-specific brochure. A variation at some hospices routinely places an *IRB-approved generic brochure* about research in hospice and palliative care in the hospice admission packet along with information about how to contact the hospice to opt-out of being screened and contacted for research, or similarly routinely provides patients and families to opt-out of being screened for research based on the local hospice's forms and policies. We will work with local hospice leadership to identify the most appropriate approach for their system. Then, a list of eligible participants will be identified and confirmed by a CITI-trained RA who will examine the daily admissions for hospice to identify participants who meet eligibility criteria among patients who have indicated interest in hearing about the study to front-line staff (or, as applicable, has not opted-out to being screened for research). This will generate a final list of eligible patient and family, and the hospice will then forward contact information to the study team among eligible participants indicating in the form of an authorization to contact form.

The Site RA will follow-up to lead recruitment efforts.

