8.3 ADVERSE EVENTS AND SERIOUS ADVERSE EVENTS

8.3.1 ADVERSE EVENTS

Any event due to the presence or progression of illness that a patient had on study enrollment will not be considered an adverse event (AE), including changes in symptoms, hospitalizations, emergency department presentations, and death more likely related to disease progression than not related to disease progression. Only events more likely not related to known underlying illness will be considered an AE.

If such an event is also related to the research and is unanticipated, regardless of its level of severity, this would require expedited (prompt) reporting to the local IRB in keeping with its reporting requirements for a suspected unanticipated problem involving risks to subjects or others (suspected UPIRTSO).

AEs are classified as to whether or not they are serious (SAE), namely life threatening (resulting in hospitalization, emergency department presentation or death), leading to permanent disability or judged a SAE by the site PI. AEs will be graded according to seriousness, and then designated as more likely expected or unexpected (yes/no), and more likely related or unrelated to the research (yes/no). Other characteristics of the AE to be recorded include date identified, diagnosis, outcome and date resolved.

SAEs will be classified as to whether or not they are a Suspected Unexpected Serious Adverse Reaction. (SUSAR) SUSARs are defined as events that are a suspected adverse reaction AND serious AND unexpected. This approach focuses the Safety Officer's and IRB's attention on potentially study participating-related events rather than on a large number of anticipated events that are part of normal disease progression and unrelated to the intervention. If a SUSAR, then expedited reporting and processes must be followed, as outlined below. If not a SUSAR, standard reporting for AEs is followed (for all AEs and SAEs), unless, as described above, the event meets the definition of a suspected Unanticipated Problems Involving Risks to Subjects or Others (UPIRTSO). An event can be a SAE, but not a SUSAR (e.g. a person hospitalized for hip fracture and not attributable to underlying known illness, but not suspected to be related to the study intervention).

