The ECC will review a pre-specified proportion of all hospitalizations and deaths. The ECC will determine if the hospitalization/death or drug related problem (DRP) was an expected event, SAE, or SUSAR. Results will be reported to the Safety Officer and the NIA Project Officer.

Cumulative aggregated AE data will be presented to the Safety Officer and the NIA Project Officer, along with tabulated outcomes data. This includes AEs, SAEs and SUSARs, plus survival, health resource utilization, and patient reported outcomes.

The Study PI is also responsible for contacting the NIH grant program officer in the event that any action resulting in temporary or permanent suspension of the trial occurs. (Because this trial does not involve any investigational medication, the action would be limited to an IRB- or investigator-initiated suspension or discontinuation of the study.)

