9.4.8 TABULATION OF INDIVIDUAL PARTICIPANT DATA

9.4.9 EXPLORATORY ANALYSES

10 SUPPORTING DOCUMENTATION AND OPERATIONAL CONSIDERATIONS

10.1 REGULATORY, ETHICAL, AND STUDY OVERSIGHT CONSIDERATIONS

10.1.1 INFORMED CONSENT PROCESS

10.1.1.1 CONSENT/ASSENT AND OTHER INFORMATIONAL DOCUMENTS PROVIDED TO PARTICIPANTS

To alleviate the burden of obtaining written consent from these typically home-bound patients and their family caregivers, we will use a telephone based consent procedure. That is, we will obtain a waiver of written documentation of informed consent for this minimal risk participation study for family caregivers and patients, since their involvement requests only access to medical records and completion of telephone questionnaires.

If a patient and family caregiver a potentially interested in study participation, they will be given a Fact Sheet by the hospice staff that summarizes the relevant information about the study, including the risks, benefits, and rights as a study participant. Hospice staff will not answer questions about the study consent, but will refer all questions to trained study staff who will be scheduled to call the patient within 1 week of referral to the study staff. The fact sheets will describe the study in detail the study intervention, study procedures, and risks.

Potentially eligible patients will be referred to the study team. To minimize burden of making a unnecessary study enrollment calls to ineligible patients, we will request a HIPAA waiver for medical record review for the express purpose of confirming eligibility by the study team. If confirmed to be eligible, the study team will call the patient and family caregiver to explain the study, answer any question about participation and the fact sheet, and to obtain telephone recorded consent.

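### Section 8.2 declares drug-related problems present at enrollment unrelated to the research, but the intervention acts on office staff and can reach a patient between hospice admission and consent

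*Combined protocol and SAP*

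**What the plan says.** Section 8.2 lists what will be monitored for safety, "including potential DRPs present upon study enrollment which, by definition, are not related to the research". The same section then gives the Event Classification Pharmacist (ECP) a monitoring task whose stated purpose is "To ensure that potential DRPs, emergency department visits, hospitalizations and deaths are indeed unrelated to the research". Section 8.3.1 asks for a yes/no judgement of relatedness for adverse events and adds: "The ECC will determine if the hospitalization/death or drug related problem (DRP) was an expected event, SAE, or SUSAR".

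The order of events comes from other sections:

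- Section 6.3 randomizes offices.
- Section 7.1 delivers the intervention to clinical staff once, at the start of the study, and to staff who join later.
- Sections 1.1 and 6.1.1 describe its content: medication review, caregiver education, and identifying and discontinuing drugs that may be inappropriate.
- Section 5.1 enrolls patients who are newly admitted to hospice.
- Section 5.5 has hospice staff offer the brochure "at their discretion within the first week after the hospice admission visit".
- Section 10.1.1.1 refers consent questions to trained study staff "who will be scheduled to call the patient within 1 week of referral to the study staff".

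Section 9.4.3 compares baseline with follow-up, within and across arms, to obtain a preliminary effect size for a larger trial.

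**The concern.** In an individually randomized trial, a problem already present at enrollment cannot have been caused by the intervention. In this trial the intervention works through staff who may already be caring for the patient, so enrollment does not mark the start of exposure.

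The harm in question is one the protocol itself names. Section 2.3.1 refers to an "additional potential risk of adverse drug withdrawal events after stopping medications". If such an event arose early and was present at enrollment, the clause would class it as unrelated by rule. Relatedness has consequences in Section 8.3.1: an unanticipated adverse event related to the research needs expedited IRB reporting whatever its severity, and SUSAR status requires a suspected adverse reaction.

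The same timing affects the secondary analysis. If staff act on the regimen before the baseline list is taken, part of any arm difference may already be in the baseline. The change from baseline would then misstate the effect meant to inform the next trial.

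**Working it through.** The plan gives no figure to reproduce. The check is the order of events, with one sum.

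**1. Can exposure precede consent?** Assignment and training happen at office level (Sections 6.3 and 7.1), and eligible patients have already been admitted (Section 5.1). Consent does not control whether medication review takes place. Section 10.1.1.1 justifies the waiver of written documentation for patients and caregivers "since their involvement requests only access to medical records and completion of telephone questionnaires". No section limits review or deprescribing to consented dyads; Section 6.1.1 reserves only the notebook and its printed contents for participants. Exposure before consent is therefore possible.

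**2. How long can the interval be?**

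- Admission visit to brochure (Section 5.5): 0 to 7 days.
- Referral to scheduled consent call (Section 10.1.1.1): 0 to 7 days.
- Sum of the stated steps: 0 + 0 = 0 to 7 + 7 = 14 days.

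Fourteen days is not a maximum, because the times from brochure to referral and from call to baseline assessment have no stated limit. It is not a typical value either, since the interval can be close to zero. For scale, the first follow-up in Section 1.3 is at 2 weeks.

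**3. Does the clause hold?** It holds for a problem that predates contact with trained staff. It does not hold for a problem that follows a drug change made between admission and enrollment in an intervention office.

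**4. Do the safety passages agree?** The Section 8.2 clause settles relatedness in advance. The ECP check later in Section 8.2, the relatedness judgement in Section 8.3.1 and the ECC classification of DRPs in Section 8.3.1 all treat it as open. None exempts problems found at enrollment, and none says it overrides the clause.

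**5. Would the reviewers see an early change?** Section 8.2 finds medication changes by comparing successive lists, so a change made before the first list is not detected that way. The enrollment record screen is described as retrospective, but no start date is given.

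**6. Which list is baseline?** Section 1.3 schedules a record-based medication list at enrollment. Section 5.1 says the eligibility variables, which include the number of medications, can be read from admission intake forms. Neither these sections nor Section 9.4.3 says whether the baseline list dates from admission or from enrollment.

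**The case against.** The strongest reply is that the clause is descriptive. It sits in a sentence saying that these problems will be monitored, and the operative steps follow: the ECP reviews potential DRPs with no stated exemption, and the ECC classifies them. The retrospective chart review of a newly admitted patient may well reach admission in practice. The clause may also mean only that the problem was not caused by the patient's own participation.

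Much of this stands. The reviews are a real safeguard, and nothing tells the reviewers to apply the clause. But the plan does not say which prevails or where the chart review starts. The innocent reading is also incomplete, because Section 8.3.1 asks about relatedness to the research, and the research includes the staff training.

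A reader might infer three stronger things that the documents do not support:

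- *That trained staff do change drugs before consent.* No passage says so. Some dyads may enroll almost at once. Others may enroll before their staff are trained, because Section 5.5 invites staff to complete the training and no passage requires completion before the first dyad.
- *That early withdrawal events will be missed or misclassified.* Monitoring continues and case review exists. The defect is a preset answer that conflicts with that review.
- *That the effect estimate is biased by a known amount or in a known direction.* The baseline list may already be close to admission, and an early effect could have either sign.

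**Conclusion.** The point holds as an internal conflict and an unsupported rule. For an intervention delivered to office staff, presence at enrollment does not establish that a DRP is unrelated to the research. The conclusion rests on the stated order of events and on the absence of any passage that ties medication review to consent. It needs no assumed effect size.

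The number of patients affected cannot be estimated from the documents. Nor can the effect on the Section 9.4.3 estimates, which come from a pilot that Section 9.2 says lacks power for efficacy. The primary feasibility endpoints are essentially unaffected. The plan should be corrected because relatedness drives expedited reporting and the change is small.

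**What to change.** **1. Section 8.2.** Delete the clause that declares enrollment DRPs unrelated. State that the enrollment chart review reaches back to hospice admission. Possible wording: *Potential drug-related problems that arose between hospice admission and enrollment will receive the same case-by-case review of relatedness as those found later.* Reconcile this with Section 8.3.1, including the roles of the ECP and the ECC. Relatedness should stay with them; Section 6.3 gives the masked adjudication team the measurement of adverse drug events and withdrawal events.

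**2. Section 9.4.3, medication outcomes.** For regimen complexity, drug count and potentially inappropriate medications, name the hospice-admission list in the medical record as baseline. Keep the enrollment list and report changes between the two by arm. This shows directly how much change preceded enrollment.

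**3. Section 9.4.3, reported outcomes.** The Hassle Scale, MQOLQ and ESAS cannot be moved back to admission. Report days from admission to baseline by arm, and state that change from baseline may be affected by earlier exposure. A follow-up comparison without baseline adjustment is not a good remedy: with one office per arm in each agency, existing differences between offices would pass straight into the estimate.

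**Cost.** Protocol wording, plus one extra medication list and a longer look-back for up to 60 patients (2 agencies × 2 offices × 15 dyads). The consent script should be checked to confirm that it covers records back to admission. The admission list will also capture the usual drug changes at hospice entry in both arms, which adds some noise.

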The study intervention is a patient-centered medication review and FCG support program called “Standardized PatiEnt-CenTered medicatiOn Review (SPECTORx) in Home Hospice”. This intervention combines 3 innovative, complementary, educational programs that, together, train hospice staff to create a comprehensive, patient-centered, medication management plan. These evidence-based tools equip hospice staff: 1. to systematically identify medications that can be stopped or tapered using STOPPFrail (Screening Tool of Older Persons Prescriptions) criteria; 2. to discontinue medications appropriately; and 3. to educate and support FCGs with medication administration and management challenges. The SPECTORx program also creates an online learning community for hospice clinicians to promote ongoing education and practice change.

[figure not shown]
Study Duration*:

Estimated study duration from earliest enrollment to completion of data collection is 12 months.

Participant Duration:

Estimated time it will take for each individual participant to complete all study-related tasks (i.e. time from enrollment to patient death, discharge from hospice, or end of study) is 6 months.

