1.2 SCHEMA

1.3 SCHEDULE OF ACTIVITIES

| STUDY PERIOD | | | | | |
|--|---|---------|---------|------------------------|----------------------|
| TIMEPOINT | Screening / Post-allocation Enrollment | | | Close-out | |
| | 2 weeks | 4 weeks | 6 weeks | 8 weeks and monthly | 24 weeks or death |
| ENROLLMENT | | | | | |
| Eligibility screening | x | | | | |
| Informed consent | x | | | | |
| FEASIBILITY | | | | | |
| SPECTORx Intervention | | | | | |
| Attention Control | | | | | |
| ASSESSMENTS (Source/Items) | | | | | |
| FCG/Demographics | x | | | | |
| FCG/Family Caregiver | x | x | x | x | x |
| Medication Administration | | | | | |
| Hassle Scale | | | | | |
| FCG/Potential medication related symptom change | | x | x | x | x |
| FCG/Patient Centered Medication Communication | x | x | x | x | x |
| FCG/Satisfaction with Care (Likelihood to recommend) | | | | | x |
| EMR/ PT Demographics | x | | | | |
| EMR/ PT Primary Hospice Admitting Diagnosis* | x | | | | |
| EMR/ PT Comorbid Illness* | x | | | | |
| EMR/PT Medications* | x | x | x | x | x |
| EMR/PT KPS* | x | x | x | x | x |
| EMR/PT Survival* | | x | x | x | x |
| EMR/PT Health resource utilization (hospital admissions, emergency department visits)* | | x | x | | x |

| | | | | | |
|---|---|---|---|---------------------------|---|
| EMR/Potential Drug Related Problem Screen | x | x | x | x | x |
| Patient/Potential Drug Related Problem | | x | | x (& monthly thereafter) | |
| Patient/MQOLQ | x | x | x | x | x |
| Patient/ESAS | x | x | x | x | x |

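### Drug-related problems and medication changes are read mainly or wholly from records kept by staff in the randomized offices, so differential recording could bias the between-arm estimates

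*Combined protocol and SAP*

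**What the plan says.** Section 8.2 makes the chart the main source for DRPs: "DRPs will be monitored by a trained research assistant who will screen the medical record using a Screening Algorithm of Potential Drug Related Problems". This happens at enrollment, every 2 weeks to 2 months, then monthly to 6 months. The screen covers clinical events, symptoms, abnormal laboratory results and drug levels, and also "new reported drug allergies or drug associated problems identified by clinicians". A second source follows: "Secondarily, a trained research assistant will also conduct a screening telephone interview with patients", at 2 weeks and monthly, with the caregiver answering if the patient cannot.

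For drugs, Section 8.2 says: "Medication changes will be identified by collecting medication lists every 2 weeks and iteratively identifying changes between lists". The Schedule of Activities (Section 1.3) lists the source as "EMR/PT Medications". I found no other scheduled source for polypharmacy, regimen complexity or inappropriate medications.

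The intervention equips hospice staff "to systematically identify medications that can be stopped or tapered using STOPPFrail" criteria (Section 1.1), and offices are randomized (Section 6.3). Section 6.3 also withholds allocation from the coordinator who collects outcomes and from the team that adjudicates drug events.

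Two items do not come from the chart. Section 1.1 measures withdrawal events by a single question on medication change since the last visit and any related symptom change. The schedule has a caregiver row, "FCG/Potential medication related symptom change", which appears to be the same item.

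**The concern.** In a cluster trial that trains clinicians, allocation can change the measuring instrument as well as the patient's care. A problem enters the chart screen only if something about it was written down, and one trigger requires a clinician to have recognised it as drug-related. A drug leaves the list only when someone updates the list. If trained and untrained offices differ in either habit, the arms will differ on these endpoints even when patients do not.

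Section 3 lists DRPs, medication changes, regimen complexity and potentially inappropriate medications among the secondary efficacy and safety endpoints. Section 9.4.3 intends the between-arm results to supply an effect size for a larger trial. DRP classifications also go to the Safety Officer (Section 8.3), who sees unblinded safety data and advises on continuation (Section 10.1.6).

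**Working it through.** **No stated figure to reproduce.** The documents give no DRP rate, charting completeness, effect size or alpha. The one related sum, 2 agencies × 2 offices × 15 dyads = 60, agrees with the stated total.

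**Do existing safeguards reach the problem?**
- *Blinding (6.3)* acts on people who read or judge the record after it is written. It cannot restore an entry never made.
- *Audit (10.1.7)* compares study data with source documents. It cannot detect an uncharted problem, or a listed drug that is no longer given.
- *Baseline comparison (8.2, 9.4.3).* Training is given once at the start of the study and to staff who join later (7.1), and patients are new hospice admissions (5.1). Trained staff may therefore already be keeping the baseline record.
- *Telephone interview (8.2)* does not depend on charting, but it is secondary and less frequent. In the first 2 months the chart has four follow-up screens (weeks 2, 4, 6 and 8). The interview has two or three contacts, depending on how the monthly schedule is read. It is also not fully arm-neutral: Section 6.1.1 lists printed guidance on what to tell the nurse and doctor, and handouts on hospice drugs, for the intervention notebook only. It does nothing for the lists.
- I found no rule for combining chart and interview findings, no reporting by source, and no check of lists against what is given at home.

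**Illustration for DRPs, no true difference.** All inputs are assumptions: true risk p = 30% in both arms; chart sensitivity c = 50% in control and 60% to 90% in intervention; interview sensitivity t = 50% in both arms; sources independent given a true problem.

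Chart only: observed = p × c. Chart or interview: observed = p × [1 − (1 − c)(1 − t)].

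| c, intervention | Chart only (control 15%) | Ratio | Chart or interview (control 22.5%) | Ratio |
|---|---|---|---|---|
| 60% | 18% | 1.20 | 24.0% | 1.07 |
| 70% | 21% | 1.40 | 25.5% | 1.13 |
| 80% | 24% | 1.60 | 27.0% | 1.20 |
| 90% | 27% | 1.80 | 28.5% | 1.27 |

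The ratios do not depend on p. The chart-only ratio is simply the ratio of the two assumed sensitivities, so it shows the mechanism and is not evidence of its size. An interview used alone would show no false difference only if it were equally sensitive in both arms.

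**Illustration for drug stops.** Assume 1.0 true stop per patient in each arm.
- Recorded 70% of the time in control and 80% to 90% in intervention: 0.7 against 0.8 to 0.9, a false excess of 0.1 to 0.2 per patient.
- Recorded 90% in control and 70% in intervention: 0.9 against 0.7, a false deficit of 0.2.

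The sign follows the assumption.

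**Scale.** With 30 per arm, a two-sided 5% test and clustering ignored, power for 15% against 27% is about 20%. A false-positive test is therefore unlikely; the harm is a biased estimate.

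**The case against.** A reader might infer that training is bound to improve charting, so that SPECTORx will look harmful on DRPs and effective on deprescribing through record-keeping alone. The documents do not support that. The modules cover medication review, caregiver support and deprescribing (6.1.1); nothing describes training in charting. Better recording is a plausible inference, not a stated effect. For the lists even the sign is open: clearing obsolete entries looks like deprescribing, but a review can also add drugs that were never listed, and some clean-up may precede the baseline list and so never appear as a change.

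The strongest points on the other side are these:
- Clinician-identified problems are one trigger among several, and a non-chart interview exists. *Stands in part:* it limits the bias for DRPs, but without reporting by source no reader can see by how much.
- Removing an obsolete order is arguably a real change in the prescribed regimen, and more recorded problems may be true detection. *Stands:* the chart alone cannot separate these from recording, which is the reason to use a second source.
- This is a feasibility pilot that disclaims power for efficacy (9.2). Caregiver burden, which Section 3 marks as the main trial outcome, is caregiver-reported. *Stands as to scope:* neither feasibility nor the caregiver burden score is affected. It does not protect the effect sizes for the record-based endpoints.

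Two stronger remedies are also tempting: making the interview the only between-arm DRP measure, or counting a stop only when a caregiver confirms it. The first relies on a source that is itself not arm-neutral. The second discards true stops when the caregiver cannot be reached or the patient has died.

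**Conclusion.** The point holds as a risk of differential ascertainment. DRPs come mainly, and medication changes entirely, from records kept by staff in the randomized offices. Differential recording could bias the between-arm estimates of DRPs, medication changes, regimen complexity and inappropriate medications, and neither blinding nor the audit removes this. The interview offsets it only for DRPs, and only in part.

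The documents do not fix the size, and the direction for the lists is uncertain. The ratios of 1.2 to 1.8 (chart only) and 1.07 to 1.27 (chart or interview) rest wholly on assumed sensitivities, on equal interview sensitivity in both arms and on independence of the two sources. The consequence is limited to secondary estimates and the safety signal. It matters because the pilot is meant to pass effect sizes to a larger trial.

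**What to change.** In Sections 8.2 and 9.4.3:

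1. Report DRPs by arm separately for the chart screen and the telephone interview.
2. Split chart-detected DRPs into those identified by clinicians and those from other triggers (events, symptoms, laboratory results, drug levels). Assign new drug allergies to one group in advance.
3. State that a between-arm difference seen only in clinician-identified chart entries will not be read as harm. Keep the full chart screen for individual safety review.
4. Compare list-derived changes, both removals and additions, with the item on medication change since the last visit, confirming that the caregiver answers it.
5. Show the medication endpoints for all list changes and, as a sensitivity analysis, for caregiver-corroborated changes only.

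The cost is SAP wording and a little more analysis; no new assessment is needed. Corroboration is limited to dyads whose caregiver responds. If the single item does not name the drug, it can corroborate only that a change occurred in the interval.
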